8.3.2 Follow-up of Adverse Events and Serious Adverse Events

After the initial AE/SAE report, the Investigator is required to proactively follow each participant at subsequent visits/contacts. All SAEs and AESIs (as defined in Section [8.3.7](#)) will be followed until resolution, stabilization, the event is otherwise explained, or the participant is lost to follow-up (as defined in Section [7.3](#)). Reasonable attempts to obtain this information will be made and documented. It is also the Investigator's responsibility to ensure that any necessary additional therapeutic measures and follow-up procedures are performed. Further information on follow-up procedures is in [Appendix 4](#).

8.3.3 Regulatory Reporting Requirements for Serious Adverse Events

Prompt notification by the Investigator to the Sponsor of an SAE (particularly life-threatening and deaths) is essential so that legal obligations and ethical responsibilities towards the safety of participants and the safety of a study intervention under clinical investigation are met.

The Sponsor has a legal responsibility to notify both the local regulatory authority and other regulatory agencies about the safety of a study intervention under clinical investigation. The Sponsor will comply with country-specific regulatory requirements relating to safety reporting to the regulatory authority, IRB/IEC, and Investigators.

Individual Case Safety Reports will be prepared for SUSARs according to local regulatory requirements and Sponsor policy and forwarded to Investigators, as necessary.

An Investigator who receives an Individual Case Safety Report describing a SUSAR or other specific safety information (e.g., Emerging Safety Issue Report, summary or listing of SAEs/SUSARs) from the Sponsor will review and file it in the Investigator's Site File and will notify the IRB/IEC, if appropriate according to local requirements.

8.3.4 Pregnancy

- Details of all pregnancies in female participants will be collected after the start of study intervention and until Safety Follow-Up.
- If a pregnancy is reported, the Investigator will record the pregnancy information on the appropriate form and submit it to the Sponsor within 24 hours of female participant pregnancy.
- While pregnancy itself is not considered to be an AE or SAE, any pregnancy complication or elective termination of a pregnancy will be reported as an AE or SAE. Adverse pregnancy outcomes (e.g., spontaneous abortion, fetal death, stillbirth, congenital anomalies, ectopic pregnancy) are considered and reported as SAEs. A spontaneous abortion (occurring at <22 weeks gestational age) or stillbirth (occurring at >22 weeks gestational age) is always considered to be an SAE and will be reported as such.
- The participant will be followed to determine the outcome of the pregnancy. The Investigator will collect follow-up information on the participant and the neonate, and the information will be forwarded to the Sponsor. Generally, follow-up will not be required for longer than 6 to 8 weeks beyond the estimated delivery date for a healthy newborn. In case of a congenital anomaly or other illness of the newborn, follow-up will continue until the illness has resolved or there is a definite outcome of the event.
- Any post-study pregnancy related SAE considered reasonably related to the study intervention by the Investigator will be reported to the Sponsor as specified in Section 8.3.3. While the Investigator is not obligated to actively seek this information in former study participants/pregnant female partner, he or she may learn of an SAE through spontaneous reporting.
- Any female participant who becomes pregnant while participating in the study will discontinue study intervention or be withdrawn from the study.

8.3.5 Cardiovascular and Death Events

Not applicable.

8.3.6 Disease-Related Events and/or Disease-Related Outcomes Not Qualifying as AEs or SAEs

Not applicable.

Asymptomatic elevations in amylase or lipase or both in participants treated with evobrutinib have been observed at a variety of time points and reported as TEAEs or noted as laboratory abnormalities. In RMS Study MS200527_0086, the incidence of TEAEs of lipase increased was slightly higher in evobrutinib 75 mg once daily and 75 mg twice daily arms (5 [9.4%] and 5 [9.3%], respectively) when compared to other arms (approximately between 4% to 6%). However, shifts from Baseline to highest grade on treatment were similar across all treatment arms for both amylase and lipase. In evobrutinib studies in other indications and in healthy participants, the incidence of TEAEs of increased amylase or lipase, or both was infrequent and no clinically meaningful differences were observed across treatment arms. Any elevation of $> 2 \times$ ULN of lipase or amylase and any type of pancreatitis are classified as AESIs.

- **Liver related events**

The elevations of transaminases observed in participants treated with evobrutinib were frequent, asymptomatic, and reversible on discontinuation of evobrutinib. The mechanism is unknown.

Evobrutinib liver AESIs will include transaminases ($> 3 \times$ ULN), bilirubin elevations ($> 1.5 \times$ ULN), biological Hy's Law cases based on laboratory data, any type of acute or chronic hepatitis (any grade), suspected drug-induced liver injury, acute or chronic hepatic failure, fibrosis, cirrhosis, and other liver damage-related conditions.

AESIs have to be reported immediately. For reporting of AESIs, see [Appendix 4](#).

8.4 Pharmacokinetics

For details on PK sampling refer to the Schedule of Assessments in Section 1.3 and [Table 1](#) for PK sampling during Part 1 and [Table 2](#) for PK sampling during Part 2.

- The following PK parameters will be calculated, when appropriate for the transporter substrates (digoxin, metformin, rosuvastatin, and sumatriptan):

Symbol	Definition
AUC _{0-∞}	The area under the concentration-time curve (AUC) from time zero (= dosing time) extrapolated to infinity, based on the predicted value for the concentration at t_{last} , as estimated using the linear regression from λ_z determination. $AUC_{0-\infty} = AUC_{0-t_{last}} + C_{last\ pred}/\lambda_z$
AUC _{0-t_{last}}	The AUC from time zero (= dosing time) to the last sampling time (t_{last}) at which the concentration is at or above the lower limit of quantification. Calculated using the mixed log-linear trapezoidal rule (linear up, log down).
AUC ₀₋₃₆	The AUC from time zero (= dosing time) to 36 hours postdose (metformin only). Calculated using the mixed log-linear trapezoidal rule (linear up, log down).
C _{max}	Maximum observed concentration.
t _{max}	The time to reach the maximum observed concentration collected during a dosing interval (the first occurrence in the case of multiple/identical C _{max} values).
t _{1/2}	Apparent terminal half-life. $t_{1/2} = \ln(2)/\lambda_z$
CL/F	The apparent total body clearance of study intervention following extravascular administration. $CL/F = Dose_{p.o.}/AUC_{0-\infty}$
V _z /F	The apparent volume of distribution during the terminal phase following extravascular administration. $V_z/F = Dose/(AUC_{0-\infty} \cdot \lambda_z)$ following single dose.
A _{e0-36}	The cumulative amount excreted from time zero (= dosing time) to the end of the collection interval after dosing, calculated for metformin only.
CLR	Renal clearance. $CLR = A_{e0-36}/AUC_{0-36}$, calculated for metformin only.

$C_{last\ pred}$ = the predicted concentration at the last sampling time, calculated from the log-linear regression line for λ_z determination.

Part 1

- Whole blood samples of approximately 4 mL per timepoint for measurement of plasma concentrations of digoxin, metformin, and rosuvastatin, will be collected on Days 1 to 4 and Days 10 to 13 ([Table 1](#)).
- Whole blood samples of approximately 2 mL for measurement of plasma concentrations of evobrutinib will be collected on Days 10, 11, 12 ([Table 1](#)).
- Urine will be collected for metformin analysis (as it is 100% eliminated by renal excretion) on Days 1 to 2 and Days 10 to 11 and an aliquot will be taken from each collection interval for concentration measurements ([Table 1](#)). The volume of urine from each collection interval will be measured.

Part 2

- Whole blood samples of approximately 2 mL for measurement of plasma concentrations of sumatriptan will be collected on Days 1 to 2 and Days 8 to 9 (Table 2).
- Whole blood samples of approximately 2 mL for measurement of plasma concentrations of evobrutinib will be collected on Days 6, 7, and 8 (Table 2).

Collection times are specified in the Schedule of Assessments (Section 1.3). The actual date and time (24-hour clock time) of each sample will be recorded to calculate actual time elapsed since the prior dose administration. For urine samples, the actual start and end date and time (24-hour clock time) of each urine fraction, as well as the volume of each urine collection fraction, will be recorded.

- The quantification of evobrutinib, digoxin, metformin, rosuvastatin, and sumatriptan in plasma samples, and metformin in urine samples, will be performed using fully validated assay methods. Concentrations will be used to evaluate the PK parameters of the transporter substrates, and evobrutinib concentrations will be summarized.
- Remaining samples collected for analyses of evobrutinib and transporter substrate concentrations may also be used to evaluate safety or efficacy aspects related to concerns arising during or after the study. Additionally, remaining plasma samples may be used for investigation of evobrutinib or transporter substrate metabolites.
- Details on processes for collection and handling of these samples are in the Laboratory Manual. Retention time and possible analyses of samples after the End of Study are specified in the respective ICF.
- PK parameters will be derived using noncompartmental methods with the validated computer program Phoenix® WinNonlin® (version 6.4 or higher; Certara, L.P., Princeton, New Jersey, USA).

The exact date and time of sample collection and study intervention administration (24-hour clock time) must be recorded in the eCRF and will be used in the calculation of PK parameters. The accepted time deviations from planned PK sampling times that will not be considered a protocol violation are listed in Table 4.

Table 4 PK Sampling Time Windows

Procedure	Time Point (Relative Time)	Window Allowance
Pharmacokinetics	Predose	- 60 min
	0.25 to 1 hours postdose	± 2 min
	> 1 to 12 hours postdose	± 5 min
	> 12 to 24 hours postdose	± 15 min
	> 24 to 72 hours postdose	± 30 min

Any deviation from the above-mentioned time windows requires a comment in the eCRF and may be discussed in the data review meeting.

CCI

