Blood sampling times (transporter cocktail)	Predose, 0.33, 0.67, 1, 1.5, 2, 3, 4, 6, 8, 10, 12, 16 hours postdose	24, 36 hours postdose	48, 60 hours postdose	72 hours postdose	Predose 0.33, 0.67, 1, 1.5, 2, 3, 4, 6, 8, 10, 12, 16 hours postdose	24, 36 hours postdose	48, 60 hours postdose	72 hours postdose
Urine sampling intervals (metformin)	Predose, 0 to 4, 4 to 8, 8 to 12 hours postdose	12 to 24, 24 to 36 hours postdose			Predose, 0 to 4, 4 to 8, 8 to 12 hours postdose	12 to 24, 24 to 36 hours postdose		
Blood sampling times (evobrutinib)					1 hour ^a	1 hour ^a	1 hour ^a	

Note: for associated sampling time windows see Section 8.4 (Table 4).

a Post morning evobrutinib dose.

Part 2: Schedule of Assessments

Assessments & Procedures	Screening	Intervention Period (Days)									Safety Follow-up	Notes	
Study Day	-28 to -2	-1	1	2	3	4	5	6	7	8	9		
Informed consent	X											Prior to any Screening activity.	
Participants resident in the CRU		< ----- >											
Eligibility criteria	X	X										For re-check of eligibility criteria on Day -1, Sections 5.1 and 5.2.	
Demography, height & weight, medical history	X											Demography to include, at minimum, age, sex, race, and ethnicity.	
Physical examination	X	X									X	Brief examination on Day -1 to check eligibility.	
Serum pregnancy test	X	X									X		
Viral serology, TSH and QuantiFERON® test	X												
Clinical laboratory tests	X	X									X	X	Details in Appendix 5.
Cotinine, drug screen, alcohol breath test, SARS-CoV-2 and FSH	X	X											FSH in postmenopausal women at Screening only.
ECG & vital signs	X	X	X								X	X	Predose
CCI													
Sumatriptan administration			X								X		Single dose, fed conditions (Sections 5.3.1 and 6.1).
PK samples sumatriptan			X	X							X	X	Table 2 and Section 8.4.
Evobrutinib administration			X	X	X	X	X	X	X	X			Twice daily, fed conditions (Sections 5.3.1 and 6.1).
PK blood sample evobrutinib								X	X	X			Table 2 and Section 8.4.
AE/concomitant medication review	X	X	X	X	X	X	X	X	X	X		X	

AE=adverse events, CRU=clinical research unit, ECG=electrocardiogram, FSH=follicle stimulating hormone, PK=pharmacokinetics, SARS-CoV-2=severe acute respiratory syndrome coronavirus type 2, TSH=thyroid stimulating hormone.

Table 2 **Part 2: PK Sampling Schedule**

Sample type	Day 1	Day 2	Day 6	Day 7	Day 8	Day 9

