Blood sampling time (sumatriptan)	Predose 0.33, 0.67, 1, 1.5, 2, 3, 4, 6, 8, 10, 12, 16 hours postdose	24 hours postdose			Predose 0.33, 0.67, 1, 1.5, 2, 3, 4, 6, 8, 10, 12, 16 hours postdose	24 hours postdose
Blood sampling time (evobrutinib)			1 hour ^a	1 hour ^a	1 hour ^a	

Note: for associated sampling time windows see Section 8.4 (Table 4).

a Post morning evobrutinib dose.

2 Introduction

Evobrutinib is an oral, selective, irreversible inhibitor of BTK which is in clinical development for the treatment of autoimmune diseases, including RMS.

Detailed information on the chemistry, pharmacology, efficacy, and safety of evobrutinib is in the IB.

There is extensive clinical experience in the use of the transporter substrates digoxin, metformin, rosuvastatin, and sumatriptan selected for this study ([Shibata 2020](#), [Stopfer 2018](#)). Full information about the potential side effects of these transporter substrates administration is described in the SmPCs for the respective compounds.

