2.1 Study Rationale

The results of nonclinical studies with evobrutinib have indicated the potential for evobrutinib to be an inhibitor of several drug transporters (e.g., OCT1, P-gp, MATE2-K, BCRP).

The intent of this study is to provide information pertaining to the effect of evobrutinib on transporter activity in humans using drug transporter substrates. The selected drug transporter substrates are well characterized ([Stopfer 2018](#), [Shibata 2020](#)) and have been established as selective substrates that are commonly used in clinical DDI studies and, except for sumatriptan (OCT1) are considered as index substrates in the most recent update of the FDA guidance and EMA guideline.

Results of this study may be used to make future recommendations regarding the concomitant administration of specific transporter substrates with evobrutinib.

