2.2 Background

Evobrutinib (also known as M2951 and MSC2364447C) is an oral, selective, and irreversible inhibitor of BTK. BTK is a crucial intracellular kinase in the B cell antigen receptor signaling pathway. The mode of action of evobrutinib and nonclinical data support clinical development in a broad spectrum of autoimmune and inflammatory disorders involving aberrant B cell and myeloid cell activity. Inhibition of BTK is expected to achieve profound B cell silencing. Thus, BTK inhibition could provide clinical benefit in the treatment of multiple autoimmune diseases including RMS.

Evobrutinib (also known as M2951 and MSC2364447C) is an oral, selective, irreversible inhibitor of BTK. Evobrutinib inhibits primary B cell responses (BCR), such as proliferation and antibody and cytokine release, without directly affecting T cells. Indirect effects on T cells can be mediated by BTK inhibition by blocking the B cell antigen presentation function. In addition, BTK inhibition blocks the activation of innate immune cells by immune complexes downstream of Fc receptor (FcR) activation. All three mechanisms may play a role in the pathogenesis of various autoimmune diseases. Thus, BTK inhibition could provide clinical benefit in the treatment of multiple autoimmune diseases including RMS.

In clinical studies with healthy participants, evobrutinib was rapidly absorbed with a t_{max} of 0.5 to 1.5 hours under fasted conditions. Evobrutinib demonstrated dose-proportional PK (i.e. C_{max} and $AUC_{0-\infty}$) over the evaluated dose range of 25 to 500 mg single dose and 25 to 200 mg once-daily multiple dose. Median $t_{1/2}$ was approximately 2 hours (range 1.8 to 2.6 hours) at relevant plasma concentrations following a single oral dose of 25 to 200 mg. Accumulation of evobrutinib is minimal with daily dosing (refer to IB).

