Evobrutinib will be dosed under fed conditions in this study. Administration of evobrutinib to healthy participants 30 minutes after the start of a high-fat or low- to moderate-fat meal resulted in a 50% to 75% increase in exposure (studies CCI [REDACTED]), and administration with a light meal (toast and coffee) resulted in a 38% increase in exposure (study MS200527_0072). Preliminary data from a recent study utilizing the current TF2 formulation demonstrated that administration of evobrutinib TF2 30 minutes after the start of a high-fat breakfast resulted in a 61% and 12% increase in AUC and C_{max} , respectively, relative to fasted conditions (study MS200527_0077). Median (range) t_{max} under fed conditions was 1.5 hours (0.5 to 3 hours).

Drug transporters

During development of NMEs, characterization of potential DDI liabilities with involvement of drug transporters is required (König 2013, Giacomini 2010, Zolk 2011). In particular, regulatory authorities request a thorough assessment of the propensity of an NME to cause DDIs by inhibition of those drug transporters with compelling clinical evidence for relevance (Hillgren 2013), including P-gp (ATP-ABCB1), OATP1B1, OATP1B3, OAT1, OAT3, OCT1, OCT2, MATE1, MATE2-K, and BCRP (ABCG2). Recently, interest in the use of the probe drug cocktail approach in transporter DDI clinical trials has increased considerably (Stopfer 2016, Stopfer 2018, Prueksaritanont 2017, Zhang 2017). Such cocktails allow simultaneous investigation of the effect of an NME on the PK of several probe drugs with different transporter specificities in a single trial, thus reducing the number of clinical DDI studies in the development program (Stopfer 2018).

Table 3 Summary of Drug Transporters and Their Index Substrates

Drug Transporter	Clinical Substrate
P-gp	Digoxin
MATE1, MATE2-K	Metformin
BCRP	Rosuvastatin
OCT1	Sumatriptan

Source: <https://www.fda.gov/drugs/drug-interactions-labeling/drug-development-and-drug-interactions-table-substrates-inhibitors-and-inducers#table2-1> (for digoxin, metformin and rosuvastatin); Chu 2018 (sumatriptan).

BCRP=Breast Cancer Resistance Protein, MATE1/2= Multidrug and Toxin Extrusion 1/2, OCT1= Organic Cation Transporter 1, P-gp=P-glycoprotein.

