2.3 Benefit/Risk Assessment

Evobrutinib

As of 31 July 2020, approximately 1,318 adult participants in 14 completed and 4 ongoing clinical studies have been exposed to evobrutinib, including healthy participants (227),

participants with RMS (261), systemic lupus erythematosus (451), or rheumatoid arthritis (363), and participants with renal impairment (31). Evobrutinib was generally safe and well tolerated in all participants. The TEAEs have been primarily mild to moderate in severity.

The evobrutinib treatment duration in this study will be 9 days (Part 1) or 7 days (Part 2), with 45 mg twice daily dosing of evobrutinib under fed conditions. This regimen was previously tested in healthy participant studies and does not exceed exposures reached in first-in-human clinical study CCI [REDACTED] where single doses of evobrutinib from 25 up to 500 mg and 14 days of dosing with 25, 75, and 200 mg/day were tested and shown to be well tolerated.

More detailed information about the known and expected benefits and risks and reasonably expected adverse events of evobrutinib may be found in Section 4.2 and the IB.

Based on the available nonclinical and clinical data to date, the conduct of the study, as specified in this protocol, is considered justifiable.

Transporter Substrates

Transporter substrates are to be administered at relatively low doses and are unlikely to cause any listed adverse event, which are provided for completeness (Section 2.3.1).

More detailed information about the known and expected benefits and risks and reasonably expected adverse events of on the transporter substrates (digoxin, metformin, rosuvastatin, and sumatriptan) may be found in the respective SmPCs.

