4.2 Scientific Rationale for Study Design

The study design and endpoints are typical for a DDI study of this type. The effect of evobrutinib on transporter activities will be investigated by measurement of the PK of the transporter substrates digoxin, metformin, rosuvastatin, and sumatriptan. Oral administration of the probe drug transporter substrates is expected to be a sensitive test for potential interactions with drug transporters such as P-gp, MATE1/MATE2-K, BCRP, and OCT1 since they reflect effects on both presystemic and systemic clearance. The transporter substrate cocktail (digoxin, metformin, and rosuvastatin) will be administered during Part 1 of the study as a reference treatment on Day 1 followed on Day 4 through Day 12 by multiple doses of evobrutinib twice daily, with a second dose of substrate cocktail given with the morning dose of evobrutinib on Day 10. During

Part 2, sumatriptan will be administered on Day 1 as reference and on Day 8, and evobrutinib will be administered twice daily on Days 2 through 8.

A single-sequence design for Part 1 and Part 2 was chosen because the exact mechanism of inhibition of the transporters by evobrutinib and therefore the time course of on- / offset of these effects are not known. Therefore, evobrutinib will be administered twice daily for 6 days before the second administration of transporter substrates in each study part.

The transporter substrate cocktail to be used in Part 1 of this study (digoxin [0.25 mg], metformin [10 mg] and rosuvastatin [10 mg]) has been optimized as a screening tool for transporter mediated DDIs (Wiebe 2020, Stopfer 2018) based on PK analyses of the substrates both separately and in combination. The safety profiles of the individual substrates of the cocktail are well established since these drugs are routinely used in clinical practice. Stopfer reported mild or moderate adverse events in 15 of 30 participants (Stopfer 2018). Similarly, for Part 2, sumatriptan (25 mg) has been recommended and used as a substrate for determining PK effects of potential OCT1 effectors (Chu 2018). The safety profile of sumatriptan is well established since it is routinely used in clinical practice (Sumatriptan SmPC).

Because some of the transporters to be investigated in this study might exist as polymorphic variants, which could affect the interpretation of the study results, samples for CCI [REDACTED] will be collected and analyzed.

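### Does a single 1 h evobrutinib sample on the interaction day leave the drug-interaction result uninterpretable?

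*Protocol*

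**What the plan says.** Protocol 1.3, Tables 1 and 2, schedule one evobrutinib sample per sampling day, at 1 hour, with the footnote "Post morning evobrutinib dose". The days are 10, 11 and 12 in Part 1 and 6, 7 and 8 in Part 2. Protocol 8.4 repeats the days ("Whole blood samples of approximately 2 mL for measurement of plasma concentrations of evobrutinib will be collected on Days 10, 11, 12" for Part 1). The interaction day is Day 10 in Part 1 and Day 8 in Part 2, so each interaction day has one evobrutinib sample.

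The parameter lists in Protocol 8.4 and SAP 16.1.5.1 name only digoxin, metformin, rosuvastatin and sumatriptan. Evobrutinib concentrations are summarized descriptively (Protocol 8.4, SAP 16.1.1), and SAP 16.1.2 has no evobrutinib parameter table.

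The primary endpoints (Protocol 3, SAP 5) are substrate AUC0-∞ and Cmax. They are estimated as with-versus-without-evobrutinib ratios with 90% confidence intervals (Protocol 9.4.3, SAP 16.1.3). Protocol 9.1 calls the analysis purely descriptive.

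On evobrutinib itself, Protocol 2.2 gives a half-life that "was approximately 2 hours (range 1.8 to 2.6 hours) at relevant plasma concentrations" and a median tmax that "under fed conditions was 1.5 hours (0.5 to 3 hours" (range in brackets). Protocol 2.3 says of the 45 mg twice-daily fed dosing: "This regimen was previously tested in healthy participant studies".

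**The concern.** An interaction study asks what happens to a substrate when the inhibitor is present, so a reader wants proof that the inhibitor was present at the intended level. Protocol 2.1 raises the stakes: "Results of this study may be used to make future recommendations regarding the concomitant administration of specific transporter substrates with evobrutinib". If a substrate ratio came out near 1, or varied widely between participants, the first question would be whether evobrutinib exposure was as expected that day.

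One sample cannot give an AUC, a peak or a terminal slope. It is also taken before the median fed tmax, so a low value in one person could mean slow absorption or low exposure. The substrates are already drawn densely on the same morning (in Part 1, "with a second dose of substrate cocktail given with the morning dose of evobrutinib on Day 10"), so a fuller evobrutinib profile looks nearly free.

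**Working it through.** **1. What the planned estimates need.** Each primary estimate is a within-participant contrast of log substrate AUC0-∞ or Cmax: Day 10 minus Day 1 in Part 1, Day 8 minus Day 1 in Part 2. Evobrutinib concentration does not enter the model. SAP 16.1.3 names only a treatment effect and a participant effect. More evobrutinib samples would change no ratio and no interval.

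**2. What supports exposure without a profile.**
- Dosing is in-house, supervised and timed, with a second staff member confirming the dose and a mouth check (Protocol 6.4).
- On substrate days, breakfast times and the share eaten are recorded (Protocol 5.3.1).
- Evobrutinib is given twice daily for 6 days before the second substrate dose (Protocol 4.2).
- The regimen was tested before in healthy participants (Protocol 2.3).
- Each participant gives three 1 h values. In Part 1 they fall on Days 10 to 12, within the period when the second substrate profile is being collected.

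**3. How informative the 1 h value is.** The documents give half-life and tmax but no concentration profile, so this step assumes one compartment with first-order absorption, dosed every 12 h to steady state. Inputs are half-life 1.8 to 2.6 h and tmax 0.5 to 3 h (both Protocol 2.2).

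ke = ln 2 / half-life. ka solves ln(ka/ke)/(ka − ke) = tmax. With interval AUC set to 1,

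C(t) = [ka·ke/(ka − ke)] · Σ over k ≥ 0 of [exp(−ke(t + 12k)) − exp(−ka(t + 12k))].

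At half-life 2 h (ke = 0.347 per h) and no lag:

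| tmax (h) | ka (per h) | C(1 h) at AUC = 1 | C(1 h)/Cmax |
|---|---|---|---|
| 0.5 | 6.07 | 0.263 | 0.89 |
| 1.5 | 1.14 | 0.199 | 0.94 |
| 2 | 0.69 | 0.151 | 0.85 |
| 3 | 0.32 | 0.099 | 0.74 |

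Ratios at equal AUC, from unrounded values:
- tmax 0.5 against 3 h: 2.65 (2.23 to 2.84 over the half-life range)
- tmax 1.5 against 3 h: 2.00 (1.80 to 2.08)
- tmax 0.5 against 2 h: 1.74
- tmax 0.5 against 1.5 h: 1.33

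Allowing an assumed lag of 0 to 0.5 h and the full half-life range, C(1 h)/Cmax is 0.85-0.95 at tmax 1.5 h, 0.67-0.86 at 2 h and 0.51-0.74 at 3 h.

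So at the median tmax the 1 h sample lies close to the peak. The large ambiguity needs one participant at the minimum of the range and another at the maximum. Protocol 2.2 gives that range directly after a high-fat breakfast result from another study. The substrate-day breakfast here is moderate-fat, about 490 calories with 13 g of fat (Protocol 5.3.1), so the extremes need not carry over.

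**4. What a fuller profile would cost and give.** Suppose evobrutinib were also assayed at nine existing draws on the interaction day (predose, 0.67, 1.5, 2, 3, 4, 6, 8 and 10 h), at 2 mL each.
- Assays per participant: 3 + 9 = 12. For 40 participants: 40 × 3 = 120 becomes 40 × 12 = 480, a fourfold rise.
- Part 1 pharmacokinetic blood: 2 × 18 × 4 + 3 × 2 = 150 mL becomes 150 + 18 = 168 mL.
- Part 2: 2 × 14 × 2 + 3 × 2 = 62 mL becomes 62 + 18 = 80 mL.

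The pharmacokinetic blood alone fits the 300 mL per 4 weeks limit in Protocol 8; safety-laboratory volumes are not stated. The gain would be descriptive Cmax, tmax and AUC0-10. The visible documents give no reference exposure for 45 mg fed, only percentage food effects (Protocol 2.2 and 4.3), so they offer nothing to judge an individual AUC0-10 against.

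**The case for a change.** The strongest case for more sampling is this. Protocol 4.2 says the mechanism of inhibition and its time course are unknown. Evobrutinib exposure depends on food, and the protocol foresees incomplete breakfasts. A participant who always absorbs slowly would show a low 1 h value on all three days, so repetition does not resolve the ambiguity for that person. The draw times already exist, a validated evobrutinib assay is planned, and the added 18 mL is modest. With those draws the sampled AUC0-10 would be 92-97% of the 12 h AUC in the same no-lag model. Protocol 4.3 also calls the dose adequate to characterize evobrutinib pharmacokinetics.

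What stands: at participant level, one time point cannot separate slow absorption from low exposure. A sponsor could reasonably choose a fuller profile.

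What does not follow is that the plan needs it. No visible objective asks for individual evobrutinib exposure, and no analysis links it to a substrate ratio. With about 16 evaluable participants per part, such a link would be exploratory. The unknown mechanism also cuts the other way: it is not established that same-day plasma AUC would explain a participant's ratio. The remark in Protocol 4.3 concerns the choice of dose and makes no sampling commitment.

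**Conclusion.** The concern does not hold as a fault in the plan. The schedule is as described, and individual evobrutinib Cmax and AUC will not be available from the planned analysis. Nothing in the visible objectives or analyses requires them, and the primary substrate ratios and their 90% confidence intervals are unaffected. Group-level exposure is reasonably supported by controlled dosing, a previously tested regimen and three 1 h values per participant.

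The remaining limitation is one of participant-level interpretation. Under the assumed model, the 1 h value at equal AUC differs about 1.3-fold between tmax 0.5 and 1.5 h, and about 2.7-fold only between the extremes of 0.5 and 3 h. Removing it would mean four times as many evobrutinib assays with no change to a planned conclusion, so sparse against full inhibitor sampling is a matter of preference.

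This rests on the one-compartment model, on a tmax range carried over from a high-fat meal, and on the visible text. Part of the objectives table is blacked out, so an exploratory evobrutinib endpoint cannot be excluded.
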